- After the screening is complete and if the potential participant is eligible, the assessment staff will explain the study in detail and ask if the person is interested in enrolling. The assessment staff will explain the study schedule, i.e. questionnaire assessments every 3 months for 12 months, plus blood samples will be collected during the BL, 6M and 12M assessments, and hair samples will be collected at BL and 12M. If the person indicates interest and willingness to enroll in the study, consent (section 1.3.4) and enrollment (section 1.3.5) must be completed in-person in a private room and may be completed at the time of referral.
- Name and ART numbers of all persons referred will be entered in a register on a daily basis. The assessment coordinator will check the screening book and sign off. At this point, the assessment team members will share any field notes from the ART Center on a daily basis with the Assessment Coordinator.
- The Assessment coordinators will assign a team member to enter the information from the screening register to the screening database on a daily basis.

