2.1 Introduction

The assessments are performed by the trained assessment team. Following are the different data collection components:

- Screening and eligibility assessment (Section 1.3.3)
- Questionnaires: Baseline, 3 month, 6 month, 9 month and 12 month follow-up
- Phlebotomy at BL, 6 months and 12 months, hair at BL and 12 months
- Electronic adherence monitoring devices
- Field notes (Maintained by assessment coordinators with details of challenges faced in the field. This can be related to recruitment, assessment, ART centers or any other part of assessment process.)

The table below outlines the assessment schedule for baseline and follow-up assessments:

Assessment	Questionnaire	Phlebotomy	Hair collection
Baseline	X	X	X
3M Follow-up	X		
6M Follow-up	X	X	
9M Follow-up	X		
12M Follow-up	X	X	X

The baseline assessment will be conducted on the same day the participant was screened and signs the consent. The baseline assessment will not be considered complete, and the person will not be considered enrolled until s/he has completed the questionnaire, phlebotomy, and hair sample collection. (Interview procedure detailed in section 2.4)

At baseline, all the participants will be provided a card with their assigned ID number. They will be informed to identify themselves according to ID numbers provided to them when they are calling the office phone numbers

Follow up dates are determined based on the baseline interview date. The interview can take place during a window of 15 days before and four weeks after this date, but the aim is to get the interview done as close to the target date as possible. If the interview cannot be completed within four weeks post the target date, the participant is considered lost to follow-up for that wave.

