2.4. Interview Procedures for 3m, 6m, 9m and 12m

Once the participant arrives at the site office, participant meets the tech team member first, to hand over the TMB device. The tech team member addresses any concerns with the device, and completes TMB related task as necessary (troubleshoot, SD card back up). Participant is then directed to the assessment team, where the interviewer will collect the study card. The study card is handed over to the data coordinator / data associate for verification.

Before administering the follow-up questionnaire, the interviewer will review tracking information with the participant to check if there are any changes in address and/or contact numbers since the last interview. If there are any changes in the tracking information a new tracking form will be filled. If there is no new information, the interviewer will make a note on the tracking form that the tracking form was reviewed and there are no changes.

After verifying and updating the tracking form, the interviewer will administer the follow-up interview the same way as outlined for the baseline questionnaire above. The 3 and 9 month follow-up visits, however, do not include blood sample collection. Hair sample collection is not to be included at 3, 6 and 9 month follow-up visits.

SECTION 3: FOLLOW-UP, TRACKING, AND WITHDRAWAL

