6.4 Hair Sampling: Schedule, Supplies, and Storage

A small sample of hair will be collected at baseline and 12 month follow-up visits

6.4.1 Materials:

- small pair of scissors
- alcohol pad
- aluminum foil (cut into ~4 inches x 4 inches and folded into quarters)
- sealable plastic bag (eg, Ziplock, 3x6"), e.g. Fisher#19240101
- thin adhesive label (for taping hair to tin foil and marking directionality)
- Study label for outside of foil packet
- hair clip (optional)

Hair should be stored at room temperature in a dark location until shipment. Hair is not a biohazardous material and can be handled with bare hands and stored accordingly.

Before sending the samples to UCSF HAL the following process will be carried out by the lab team:

- The ID numbers for which the hair samples are due to be sent to the UCSF HAL will be identified and printed out
- The hair samples will be segregated as per waves for each site and will be packed and sealed in separate envelopes as per the list.
- All the small envelopes will be transferred to a larger envelope.
- The Lab coordinator will write the number of envelopes inside the larger envelopes and sign off.
- The Project Manager cross checks all the details including the packing and after this the envelope is sealed off and handed over to the UCSF team member visiting the India office.

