6.4.2 HAIR COLLECTION PROCEDURE

(Detailed Instruction Manual With Pictures Is Available In Appendix)

Small samples of scalp hair are collected in the manner described:

Materials required: Scissors, piece of tin foil, patient labels (2), ziplock bag, alcohol swabs, and desiccant pellet

Suggest making these “hair kits” ahead of time

Step 1: Clean the blades of a pair of scissors with an alcohol pad and allow blades to completely dry

Clean off blades of scissors between patients

Step 2: Lift up the top layer of hair from the occipital region of the scalp. Isolate a small thatch of hair (~100 fibers of hair at the baseline visit; 50 strands of hair for subsequent visits) from *underneath* this top layer of hair from the occipital region. (A hair clip can be used to keep the top layer of hair out of the way).

Can use hair clip to keep top layer of hair away if easier

Step 3: Cut the small hair sample as close to the scalp as possible

STRAIGHT HAIR

CURLY HAIR

SHORT HAIR

Can let hair fall directly into piece of tin foil when very short/cropped (no need to label end since too short)

BRAIDED HAIR

Cut hair thatch from in-between braids or dread locks

Step 4: Keep your fingers on the part of the hair that was FURTHEST away from the scalp and put the hair sample down on an unfolded piece of tin foil

Step 5: Put a thin label over the end of the hair sample that was FURTHEST away from the scalp

If hair very short just let it fall into the piece of tin foil and no need to label the distal end

Step 6: Refold the foil over to completely enclose the hair and place a study ID label on the folded piece of foil

Step 7: Place the folded piece of foil inside the plastic (e.g. Ziplock®) bag (desiccant pellet in the bag is optional) and seal the bag;

Good collection: Distal end (side farthest from scalp) labeled

Bad collection: Distal end could have been labeled (long enough) but not

Okay not to label because too short

Hair samples should be kept at room temperature and in a dark place prior to shipment. Hair samples are collected by Principal Investigator ([name]) during her visit to the study site and brought to UCSF.

Once the hair samples have been received by the UCSF project manager, the UCSF statistician prepares a list with the regimens of the corresponding participants. An appointment is made for a representative from the Hair Analysis Lab to come pick up the hair samples in person. The list with the regimens is emailed to this person.

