Laboratory assays for hair concentrations conducted at UCSF:

The hair samples are delivered to the UCSF Hair Analytical Laboratory where nevirapine (NVP) and Efavirenz (EVF) is extracted and analyzed with liquid chromatography/tandem mass spectrometry (LC/MS/MS) using validated methods approved by the Division of AIDS' Clinical Pharmacology and Quality Assurance Program.

- The proximal section of the thatch of hair (generally about 1-2cm, depending on duration of exposure to be assessed) is cut down and chopped to 1-2 mm length segments and 5 mg is weighed and processed.
- NVP and EFV are extracted with (methanol : trifluoacetic acid (9:1) for NVP) solution and internal standard in a 37°C shaking water bath overnight (>12 hours), followed by extraction with 3.00mL methyl *t* *ert*-butyl ether/ethyl acetate (1:1) under weak alkaline conditions and then analyzed by LC/MS/MS.
- The LC/MS/MS procedure separates NVP And EFV by utilizing a Micromass Quattro LC system equipped with a Hypersil BDS C18 column (4.6 x 100 mm, 5 μ m particle size), a mobile phase system consisting of acetonitrile : water : acetic acid (50 : 50 : 0.15) (v:v:v) with 4 mM ammonium acetate for NVP and acetonitrile/water (65:35) (v:v) for EFV and mass spectrometric detection with positive ionization for NVP and negative ionization for EFV by ESI (Electrospray Ionization) and mass scanning by MRM (Multiple Reaction Monitoring) analysis.
- Data processing will be performed using Analyst data acquisition software.
- The relative error (%) and precision (coefficients of variation) for spiked quality control hair samples at low, medium and high concentrations are all <15%.
- A detailed methods paper on using LC/MS/MS analysis for EFV on is available at DOI: 10.1002/rcm.3750

SECTION 7:: TEL-ME-BOX PROCEDURES

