Trial number: NCT03086655

Tel-Me-Box:

Testing a New, Real-time Strategies for Monitoring HIV Medication Adherence in India

Statistical analyses Plan:

This is a feasibility trial of automated reminders from an electronic pillbox (the Tel-Me-Box). Feasibility analyses will include tabulation of preference for the different kinds of reminder available. Further descriptive analyses will include calculation of enrollment and retention rates over the 12-month follow-up period.

To assess if tailored real-time adherence feedback via Tel-Me-Box shows potential to improve adherence, we will compare adherence from Tel-Me-Box (quarterly assessment for 12 months), as well as HIV viral loads, and hair ARV levels (both every 6 months) in the intervention (Tel-Me-Box with reminder) and control groups (Tel-Me-Box without a reminder). We will also compare self-reported adherence (assessed quarterly) between the 2 arms. Differences between the two groups in change in the outcomes over time will be assessed via the interaction between time and group in GEE linear or logistic regression models, for continuous and categorical versions of the outcome variables, respectively. Count variables will be analyzed via Poisson or negative binomial regression, depending on absence (Poisson) or presence (negative binomial) of overdispersion in the data distribution. Robust standard errors will be used in cases of deviation from normality in the linear regression models. *Note that these analyses are for illustration purposes only, as these were not the primary analyses this pilot study was powered for.*

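### The SAP says hair drug levels are measured every 6 months, but the protocol collects hair only at baseline and 12 months; the one hair contrast that remains should be adjusted for baseline.

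*SAP*

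**What the plan says.** The SAP lists the between-arm comparisons as device adherence (quarterly) "as well as HIV viral loads, and hair ARV levels (both every 6 months"), plus self-reported adherence. Differences in change are to be tested by the time-by-group interaction in GEE models: linear for continuous versions of an outcome, logistic for categorical versions. Robust standard errors are used if a linear model departs from normality. The SAP adds that these analyses are illustrative and are not what the pilot was powered for.

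The protocol gives a different hair schedule in four places:

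- Section 1.3.3, the explanation given to eligible people: "hair samples will be collected at BL and 12M".
- Section 2.1: "Phlebotomy at BL, 6 months and 12 months, hair at BL and 12 months". The table there agrees.
- Section 2.4: "Hair sample collection is not to be included at 3, 6 and 9 month follow-up visits".
- Section 6.4: "A small sample of hair will be collected at baseline and 12 month follow-up visits".

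Three other places bear on the analysis. Section 2.1 says a person "will not be considered enrolled until s/he has completed the questionnaire, phlebotomy, and hair sample collection". Section 6.4.2 names two analytes: "nevirapine (NVP) and Efavirenz (EVF) is extracted and analyzed with liquid chromatography/tandem mass spectrometry (LC/MS/MS"). The same section says that, once samples arrive, "the UCSF statistician prepares a list with the regimens of the corresponding participants", and that this list goes to the hair laboratory. Section 1.4 randomises separately within each of the two sites.

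**The concern.** Hair concentration is the first outcome named in Aim 3 (protocol section 1.1), whose purpose is a preliminary estimate of effect. The SAP misstates when that outcome is measured. Once the schedule is corrected, the general repeated-measures model shrinks to a comparison of change scores, which does not make the best use of the baseline sample.

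The SAP also leaves open how this single contrast is to be computed. It gives no scale or cut-point for hair, and no rule for two separately assayed drugs in a trial open to anyone on ART (section 1.2). The regimen list exists, but the documents use it only for the laboratory. Nothing says how it decides who has a usable value, or how a drug that was never prescribed is told apart from a prescribed drug at a low level.

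At stake are the width and the meaning of the hair estimate, not the validity of a confirmatory test.

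**Working it through.** **1. The schedules side by side.**

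| | Baseline | 6 months | 12 months |
|---|---|---|---|
| Viral load, SAP | yes | yes | yes |
| Viral load, protocol | yes | yes | yes |
| Hair, SAP | yes | yes | yes |
| Hair, protocol | yes | no | yes |

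The planned enrolment reproduces: 2 arms × 60 = 120, and 2 sites × 30 = 60 per arm. The SAP wording implies 120 × 3 = 360 hair samples; the protocol yields 120 × 2 = 240. The documents give no power calculation to reproduce.

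**2. What the SAP's model becomes for hair.** With two time points, the time-by-group term is

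(mean at 12 months − mean at baseline, intervention) − (the same, control).

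In 300 simulated complete datasets, the interaction from an exchangeable GEE equalled this difference in mean change to within 3 × 10⁻¹⁶.

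**3. Precision of change against baseline adjustment.** Let both time points have variance σ², let ρ be their correlation, and let n be the number per arm.

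- Change: variance of the arm difference = (2/n) × 2σ²(1 − ρ).
- Regression on baseline (ANCOVA): (2/n) × σ²(1 − ρ²).
- Ratio, ANCOVA to change: (1 − ρ²) / [2(1 − ρ)] = (1 + ρ)/2.

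The documents give no ρ, so a range is shown.

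| Assumed ρ | Variance ratio | n per arm for change to match 60 |
|---|---|---|
| 0.3 | 0.65 | 60/0.65 ≈ 92 |
| 0.5 | 0.75 | 60/0.75 = 80 |
| 0.7 | 0.85 | 60/0.85 ≈ 71 |

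**4. The gain does not depend on the scale.** With unequal variances σ₀² (baseline) and σ₁² (12 months), the per-person change variance minus the ANCOVA variance is

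(σ₀² + σ₁² − 2ρσ₀σ₁) − σ₁²(1 − ρ²) = (σ₀ − ρσ₁)² ≥ 0.

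Apart from the small cost of estimating the slope, ANCOVA is never less precise, on the raw or the log scale.

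**5. Size on a log scale, under assumptions.** Take log-SD 0.8, so σ² = 0.64, with ρ = 0.5 and n = 60.

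- Change: SE = √(2 × 0.64/60) = 0.146; 95% CI factor exp(1.96 × 0.146) = 1.33.
- ANCOVA: 0.75 × 0.64 = 0.48; SE = √(2 × 0.48/60) = 0.126; factor 1.28.
- ANCOVA with 90% or 50% evaluable (54 or 30 per arm): factor 1.30 or 1.42.

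The following simulations use the same inputs with an assumed effect of 0.35 log units, half of participants on each drug, and equal drug levels unless stated.

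- Power rises from about 67% (change) to 77% (ANCOVA) on the log scale, and from about 53% to 62% on the raw scale.
- If one drug's levels are 10 times the other's, the drug term takes log ANCOVA from 69.5% to 77.6%.
- The site term gains nothing if sites have equal levels. At an assumed site difference of 0.6 log units it takes the SE from 0.130 to 0.127.

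**6. Where the scale does matter.** Suppose 10% of 12-month values in both arms sit 3 log units below the median, as a cluster of non-takers might, and are set to half the assay limit. The table gives power.

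| Drug levels | Log ANCOVA | Raw change |
|---|---|---|
| Equal | 33% | 43% |
| 10-fold apart | 32% | 27% |

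The log scale with half-limit substitution is therefore not reliably better than the raw scale.

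**The case against.** The strongest reply is that correcting one phrase changes no result, that the comparisons are labelled illustrative, and that preferring ANCOVA to change is taste: in the worked example the CI factor moves only from 1.33 to 1.28. The first two parts stand and hold the grade at minor. The third does not. The gain follows from the algebra, not from a modelling preference, and it needs no extra sample.

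Four further objections limit the point:

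- A reader might infer that the SAP pools raw nevirapine and efavirenz values, so that the drug with the higher level dominates. The SAP does not say so. It speaks of levels in the plural and allows categorical versions, so figures for raw pooling describe a hypothetical analysis.
- A reader might infer that the log scale is simply right. It gains precision if levels are log-normal. But entry requires self-reported poor adherence or repeated treatment interruptions (section 1.2), so a cluster of very low values is plausible, and step 6 shows what that does. The protocol states no assay limit.
- A baseline hair sample is not the same as a baseline level. Someone on neither assayed drug has no usable value. Section 1.3.5 also counts a person as enrolled at consent, unlike section 2.1. But section 1.4 randomises at completion of baseline, and section 2.1 requires hair for that, so randomised participants should at least have the sample.
- Restricting the analysis to people on the same assayed drug at 12 months selects on something that happens after randomisation and may bias the estimate. That is a trade-off to declare, not a settled rule.

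**Conclusion.** The schedule contradiction is certain: the current texts of the two documents disagree, and protocol section 2.4 excludes 6-month hair in words. The case for baseline adjustment is also firm. Its size depends on an unknown correlation: the variance falls to 0.65 to 0.85 of the change-score variance for correlations of 0.3 to 0.7. High confidence applies to these two parts only. The scale and the handling of drugs and low values are missing detail, for which the documents do not point to one right answer.

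Three stronger readings are not supported:

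- **That the trial is underpowered for hair.** No target effect, SD or power is stated, so no shortfall can be computed. The simulated powers only compare methods under assumed inputs.
- **That the planned analysis is invalid.** In simulation with no true effect, even a raw change analysis with unequal-variance standard errors rejected 4.7 to 4.9% of the time.
- **That the absent 6-month sample must cost precision.** For a straight-line trend with exchangeable correlation it costs none: the sum of squared time deviations is 36 + 0 + 36 = 72 with it and 36 + 36 = 72 without. What is lost is the 6-month contrast and the shape over time.

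Severity: minor.

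**What to change.** 1. Correct the SAP to hair at baseline and 12 months. Keep six-monthly for viral load.
2. For the continuous hair outcome, replace the time-by-group term with a regression of the 12-month level on arm, baseline level, assayed drug (nevirapine or efavirenz) and site, with robust standard errors. Report the estimate with its 95% CI.
3. Compare levels within drug, using the regimen list. Do not count a drug that was not prescribed as a low level. Report evaluable counts by arm at baseline and 12 months. State how regimen changes are handled and that any 12-month restriction is post-randomisation.
4. State in advance the scale, any cut-point for a categorical version, and the handling of values below the assay limit. Present these as choices, with a sensitivity analysis on the alternative scale.
5. Keep the illustrative label.

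The cost is one corrected phrase, a few SAP sentences and a small count table, with no new visits or samples. The interval widens as fewer participants are evaluable (step 5), and the 6-month hair information is not recovered.

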Trial number: NCT03086655

Tel-Me-Box:

Testing a New, Real-time Strategies for Monitoring HIV Medication Adherence in India

PROTOCOL

July 2, 2021

Table of Contents

SECTION 1: OVERVIEW.....	1
1.1 Aim 3	1
1.2 Eligibility.....	1
1.3 Recruitment, Screening and Enrollment	1
1.4 Randomization To Intervention Or Control Arm	3
SECTION 2: ASSESSMENT: BASELINE AND FOLLOW-UP.....	5
2.1 Introduction.....	5
2.2. Pre-Interview Procedures for All Waves.....	5
2.3. Baseline Interview Procedures:	6
2.4. Interview Procedures for 3m, 6m, 9m and 12m	8
SECTION 3: FOLLOW-UP, TRACKING, AND WITHDRAWAL	9
3.1. Identifying and Scheduling Participants for Follow-Up.....	9
3.2. Procedures for Making Follow-Up Calls	9
3.3. Home and Workplace Tracking and Assessment Visits:.....	11
3.4 Participant Withdrawal, Loss to Follow Up or Death	13
SECTION 4: DATA MANAGEMENT.....	16
4.1 Data Entry Procedures	16
4.2 Data Entry Verification	17
4.3 Data Upload Procedure and UCSF Review:.....	17
4.4. Data Storage / Maintaining Confidentiality	18
4.5. Data Backups.....	18
4.6 Data from TMB (Devices)	18
4.7 Data for Phlebotomy Lab Samples from RLS.....	18
SECTION 5: PHLEBOTOMY AND LAB PROCEDURES.....	20
5.1 Overview	20
5.2 Procedures	20
SECTION 6: HAIR COLLECTION AND LAB PROCEDURES	25
6.1 Hair Collection and Storage Tasks.....	25
6.2 Hair Collection Quality Control Procedures.....	25
6.3 Data	25
6.4 Hair Sampling: Schedule, Supplies, and Storage	25
SECTION 7:: TEL-ME-BOX PROCEDURES	33
7.1 TMB Procedures	33

7.2. TROUBLESHOOTING PARTICIPANTS' TMB BOX PROBLEMS.....	35
7.3 Device Return for Withdrawn Participants	38
APPENDIX A: TMB TRACKING FORM.....	39

SECTION 1: OVERVIEW

1.1 Aim 3

To perform a pilot RCT to estimate the effect of real-time adherence feedback delivered wirelessly through the Tel-Me-Box on hair ARV concentrations, device-monitored adherence and viral load suppression in adherence-challenged patients. Among adherence challenged-patients at SJRI without virologic resistance, this pilot will produce a preliminary estimate of the effect of real-time, wireless adherence feedback delivered in a tailored fashion via Tel-Me-Box on hair ARV concentrations, device-monitored adherence and virologic suppression compared to patients (60 in each arm) using Tel-Me-Box without real-time feedback.

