1.2 Eligibility

Potential participants must meet the following inclusion criteria to be considered:

- 18 years of age or older
- HIV-positive
- Currently on ART
- Speak one of the local languages
- Able and willing to participate in the study, provide informed consent, contact information, and express a willingness to return for follow-up visits as per the study schedule for the next 12 months.
- Adherence-challenged per self-report, i.e. report of <90% ART adherence or >2 ART treatment interruptions of at least 2 days in the past 3 months.
- Not used or participated in one of our previous studies, using AMD/TMB
- Live within 100 km of study site

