1.4 Randomization To Intervention Or Control Arm

At the completion of baseline (see 2.3 for details), participants will be randomized to intervention or control arm. At each site, half of the participants will form the intervention group and the remaining participants will form the control group. The UCSF statistician will use a random number generator (<https://www.randomizer.org/>) to randomly pick half of the 60 ID numbers from one site and put them into one group. The 30 non-chosen numbers will form a second group, The statistician will then randomly decide which group will be assigned to the control group and which one to the intervention group. The process will be repeated for the other site.

This randomized set of ID numbers will be shared with the intervention team (tech team) at each site and they will assign the next available ID on the list, thereby randomizing the participant, at the time of completion of baseline. The tech team will prepare the TMB device according to the intervention arm allocated and give the participant the TMB device (see section 7.1.4 for details below). The assessment team will be blinded to the allocation.

SECTION 2: ASSESSMENT: BASELINE AND FOLLOW-UP

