4.6 Data from TMB (Devices)

The data will be available on a secure website, and downloaded and uploaded by the Project Engineer which will be reviewed monthly by the UCSF statistician.

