7.1.4 Assigning the Box to the Participant (Baseline)

1. Intervention arm: Once participant is enrolled and assigned to intervention arm, details of pill intake time is collected by tech team member present at the ART center and this is communicated to the tech team coordinator via whatsapp group. Tech coordinator connects the device to the laptop and Tech engineer gains access to the system via TeamViewer (remote desktop viewer) to code the pill intake timing for the device. The device is then tested remotely by tech engineer to make sure the coding for pill intake time is working. The coded device is handed over to the participant by the tech team member at the site office.
2. Control arm: TMB device with no reminders will be handed over to the participant by the tech team member.
3. During the assignment of the device, a small document which describes the usage of the box is handed over to the participant. The participant is free not to carry this document in case they are not comfortable carrying it home. The participant will then be given instructions on how to use the TMB. The tech team (intervention team) staff will need to clarify all queries the participant may have about the TMB. The queries asked here need to be documented and shared with the assessment coordinator and tech coordinator on a daily basis which will be in turn discussed during the upcoming assessment and tech meetings.
4. Once the tech team has assigned the devices to enrolled participants, they will add the device to the website.
5. In the absence of the tech team member, the Project Engineer will carry out this task remotely. A team member will update the device assignment in the whatsapp group before logging out from the site. Tech Team coordinators will add the ID in segregation and keep it updated on a daily basis.
6. The log can be accessed by the Tech team members, Project engineer and study managers. Device related information like sim card, type of network and imei number of device is saved in an excel format and is maintained by the Project Engineer which uploaded to the UCSF box on a weekly basis.

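### Tel-Me-Box adherence exists only after randomisation, so the planned time-by-group interaction does not estimate the reminder effect on it; an immediate, lasting benefit gives an interaction of zero

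*SAP*

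**What the plan says.** Aim 3 (Protocol section 1.1) states that "this pilot will produce a preliminary estimate of the effect of real-time, wireless adherence feedback" and lists device-monitored adherence among its outcomes.

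The SAP plans to compare Tel-Me-Box adherence, taken quarterly over 12 months, between the arms, along with viral load, hair drug levels and self-report. The method is the same for all of them: "Differences between the two groups in change in the outcomes over time will be assessed via the interaction between time and group", fitted "in GEE linear or logistic regression models, for continuous and categorical versions of the outcome variables, respectively". It does not say whether time is linear or categorical, or where its zero lies. It ends with a caveat: "Note that these analyses are for illustration purposes only, as these were not the primary analyses this pilot study was powered for".

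The Protocol fixes when device data begin. Randomisation follows completion of baseline, and then "The tech team will prepare the TMB device according to the intervention arm allocated and give the participant the TMB device" (section 1.4). In the intervention arm the pill times are programmed and tested first, and "The coded device is handed over to the participant by the tech team member at the site office" (section 7.1.4). Earlier users of the device cannot enrol; the criterion reads "Not used or participated in one of our previous studies, using AMD/TMB" (section 1.2). No run-in without reminders is described.

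**The concern.** A time-by-group interaction estimates a treatment effect when the first time point precedes treatment: the arms start level, and any later divergence is the effect. Self-report, viral load and hair levels have such a starting point, because questionnaire, blood and hair are all collected at baseline (section 2.1). Device adherence does not. Its first value already includes up to three months of reminders in one arm and none in the other, so the interaction removes whatever part of the effect is present from the start.

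Reminders could plausibly work from the first day and then hold or wane. In the first case, the quantity the SAP names would present a real, sustained benefit as no effect. In the second, with linear time, it would carry a negative sign although adherence is better with reminders in every quarter. Later work building on this pilot would take the wrong message from an outcome that the reminders act on directly.

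**Working it through.** The documents give no SD, correlation, effect size or significance level for device adherence, so there is no planned figure to reproduce. The first two steps are algebra; the rest rests on stated assumptions.

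**Inputs from the documents.** 60 per arm (Protocol section 1.3.1); four quarters of device data (SAP); no device value before allocation (Protocol sections 1.2, 1.4 and 7.1.4).

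**Assumptions.** SD 25 percentage points (range 20 to 30), equal within-person correlation ρ = 0.6 (range 0.4 to 0.8), two-sided 5% test, normal approximation, no missing data.

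**Step 1: constant benefit.** Let the control mean in quarter t be m(t) and the intervention mean m(t) + d on the model's scale. The gap is d in every quarter.
- Linear time: the slope of the gap is 0.
- Categorical time: each contrast with the first quarter is d − d = 0.

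This holds for any m(t), SD or correlation, and on the identity or logit scale if the benefit is constant on that scale. With d = 10 the group term is 10 and the interaction 0. A constant odds ratio of 1.8 also gives a logit interaction of 0.

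**Step 2: is this specific to the device outcome?** Add a baseline with no gap, followed by +10 at 3, 6, 9 and 12 months. The linear interaction becomes +0.67 points per month, no longer zero. The missing pre-randomisation value is what causes the problem.

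**Step 3: constant +10 points, precision and power.** The averaged arm difference has

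SE = SD × √[(2/60) × (1 + 3ρ)/4] = 25 × √[(2/60) × 0.70] = 3.82 points.

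- 95% CI half-width = 1.96 × 3.82 = 7.5 points (range 5.3 to 9.9).
- Power for 10 points = 75% (range 51% to 96%).
- The interaction is significant 5% of the time, which is the false-positive rate.

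**Step 4: benefit fading linearly from +15 to +5 points.** The gaps are 15, 11.7, 8.3 and 5 (mean 10), so the slope is −10/3 = −3.33 points per quarter.

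Slope SE = SD × √[(2/60) × (1 − ρ)/5] = 25 × √[(2/60) × 0.08] = 1.29.

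- Linear time: significantly negative 73% of the time (range 42% to 99.5%).
- Categorical time: the 3-df test has noncentrality (3.33/1.29)² = 6.67 and rejects 57% of the time (range 28% to 98%), with no direction attached.

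**Step 5: does the group term fill the gap?** In the linear-time interaction model it is the gap where time equals zero. For the fade in step 4:

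| Coding of quarters | Group term (points) |
|---|---|
| 1 to 4 | 15 + 3.33 = 18.3 |
| 0 to 3 | 15 |
| centred | 10 |

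**Simulation check.** In 10,000 simulated trials at SD 25 and ρ = 0.6, a constant benefit gave a significant slope in 5.0% and a significant averaged difference in 74%. Under the fade, the slope was significantly negative in 73%.

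**The case against.** The strongest reply is that this is a feasibility pilot whose SAP labels these analyses illustrative and attaches no decision to them. The SAP also says it will compare device adherence between arms, which could be read to include a difference in level, and it has a separate sentence on count models that mentions no interaction. Quarter-specific differences can be derived from the same fit. Under a constant benefit the group term equals the benefit however time is coded. A negative interaction under fading correctly describes waning and misleads only if read as the overall effect.

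Much of this is right, and it limits the consequence. It does not remove the gap. Neither the general statement nor the count-model sentence names an effect measure. The group term is unambiguous only if the gap is constant, which nobody knows in advance. The illustrative label excuses low power, but not the naming of a quantity other than the one Aim 3 asks for.

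The zero also has a condition: the benefit must be constant on the model's scale. A constant 10-point risk difference over a control rate falling from 75% to 60% gives a logit interaction of −0.021 per month. That is not zero, but it does not measure the benefit either. Finally, an equally weighted average is one reasonable summary among several; what matters is that a difference in level is named.

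**Conclusion.** The concern holds, for Tel-Me-Box adherence only. Every quarter of device data is on treatment, and the one between-arm quantity the SAP specifies measures change in the arm gap, not the reminder effect. That the expected interaction is zero under a benefit constant on the model's scale needs no assumption about variability or time coding. The power figures and the interval width do depend on the assumed SD, correlation and effect pattern; dropout or periods with the device offline would change them. The negative sign under fading also requires linear time, which the SAP leaves open. The point should be fixed, although no decision rule depends on it: following the plan as written could report a sustained benefit as null.

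**What to change.** Add two or three sentences to the SAP for Tel-Me-Box adherence:

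- The effect measure is the between-arm difference averaged over the four quarters, with quarter as a category, reported with a 95% CI.
- Each quarter's between-arm difference is reported with its 95% CI.
- The time-by-group interaction is kept as a secondary description of persistence or waning, with the coding of time stated.

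Adjusting for site and baseline self-reported adherence is optional and may improve precision.

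This needs no new data or participants. The change should be dated and documented against the review of device data, "which will be reviewed monthly by the UCSF statistician" (Protocol section 4.6), so that a reader can see what had been seen when the effect measure was chosen.
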